Study Statistical Methods	
Angiographic Exclusion Criteria
 
20. Failure to treat clinically significant inflow lesions in the ipsilateral iliac, femoral, or popliteal arteries with <math>\leq 30\%</math> residual stenosis, and no serious angiographic complications (e.g., embolism).
 
21. Failure to successfully treat significant non-target infra-popliteal lesions prior to treatment of target lesion(s). Successful treatment is defined as obtaining <math>\leq 50\%</math> residual stenosis with no serious angiographic complications (e.g., embolism).
 
22. Treatment of vessels below the ankle joint.
 
23. Failed pre-dilatation in target lesion during index procedure with angiographic evidence of serious angiographic complications.
 
24. Target lesion includes in-stent restenosis.
 
25. Evidence of aneurysm or thrombus in target vessel.
 
26. No calcium or mild calcium in the target lesion.
 
27. Target lesion within native or synthetic vessel grafts.
 
28. Failure to successfully cross the guidewire across the target lesion; successful crossing defined as tip of the guidewire distal to the target lesion in the absence of flow limiting dissections or perforations.
 
 
Intent-to-Treat (ITT) analysis with pre-defined subgroups (e.g., renal failure)
 

	No.: CP 65007	REV. C
	TITLE: Disrupt PAD BTK II Study	
	CLASS: CLINICAL PROTOCOL	PAGE 12 OF 71

	
 
Designed to assess exact 95% confidence interval (CI) for primary endpoints; no formal hypothesis testing
 

Study Sponsor/Study Management	
Shockwave Medical, Inc. [name] [name] USA
 
Contact: [name] Title: Senior Clinical Research Manager Telephone (direct): [contact] Email: [contact]

EU Legal Representative	
Medpace Finland OY [name] Finland

EU Authorized Representative	
ICON (LR) Limited [name] Ireland

Study Principal Investigators	
[name], FACC Medical Director Interventional Cardiologist, Advanced Heart and Vein Center [name] [name] Clinical Associate Professor, Division of Vascular Surgery Stanford University Medical Center [name] USA

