### 5.2 Secondary Endpoints

- Serious angiographic complications (flow-limiting dissection, perforation, distal embolization, or acute vessel closure) as assessed by the angiographic core lab
- Lesion Success defined as final residual stenosis  $\leq 50\%$  in the target lesion without serious angiographic complications as assessed by the angiographic core lab
- Primary Patency at 6 and 12 months as assessed by both subject and lesion level defined as the absence of both total occlusion (100% diameter stenosis as assessed by DUS core lab) in all of the target lesions in a flow pathway, as well as any CEC adjudicated Clinically-Driven Target Lesion Revascularization (CD-TLR)
- Clinically-Driven Target Lesion Revascularization (CD-TLR), CEC adjudicated, at 30 days, 6, 12, & 24 months
- Major Adverse Events (MAE), CEC adjudicated, at 30 days defined as a composite of:
  - Need for emergency surgical revascularization of target limb
  - Unplanned target limb major amputation (above the ankle)
  - Symptomatic thrombus or distal emboli that require surgical, mechanical, or pharmacologic means to improve flow, and extend hospitalization

	No.: CP 65007	REV. C
	TITLE: Disrupt PAD BTK II Study	
	CLASS: CLINICAL PROTOCOL	PAGE 20 OF 71

- Perforations that require an intervention, including bail-out stenting
- Quality of Life (QoL) assessed by VascuQoL questionnaire at 30 days, 6, 12, & 24 months, reported as change from baseline
- Major Target Limb Amputation, CEC adjudicated, at 30 days, 6, 12, & 24 months
- Ankle-brachial index (ABI) or toe-brachial index (TBI) at 30 days, 6, 12, & 24 months, reported as change from baseline
- Rutherford Category at 30 days, 6, 12, & 24 months, reported as change from baseline
- Number of existing, new, and recurrent wounds at 30 days, 6, 12, & 24 months
- Number of healed wounds at 30 days, 6, 12, & 24 months
- Number of non-healed wounds by category (improving, stagnant, worsening) at 30 days, 6, 12, & 24 months

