### 9.1 General Statistical Methods

Descriptive statistics will be provided in this clinical study. Analyses will be conducted at pre-specified time points including 30 days, 6, 12 and 24 months.

Categorical variables will be summarized by the number of observations available, frequency, and percentage. Unless otherwise noted, missing data will be excluded from the denominator. Comparisons will utilize a Chi-square test, or Fisher's exact test when 20% or more of expected cell frequencies are less than 5. Clinical outcomes analyzed at 30 days will be evaluated as categorical (binary) data. McNemar's chi-square may be used to assess within-subject changes in a bivariate response variable. Exact confidence intervals will be generated for estimates of proportions.

Continuous variables will be summarized by the mean, standard deviation, median, minimum, and maximum. Within-subject changes will be analyzed parametrically using the Paired t-test if the differences are normally distributed, or non-parametrically using the Sign-Rank Test if the differences are not normally distributed. Asymptotic confidence intervals will be generated for estimates of means.

Exploratory analyses and clarifications to the protocol specified analysis plan will be documented in the SAP. Statistical analyses will be performed using SAS System® Version 9.4 or higher.

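### The normality switch in section 9.1 can put a signed-rank p-value beside a confidence interval for the mean, and with skewed changes the two can contradict each other

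*Combined protocol and SAP*

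**What the plan says.** Section 9.1 (General Statistical Methods) sets the rule for change scores in its paragraph on continuous variables. The first branch is: "Within-subject changes will be analyzed parametrically using the Paired t-test if the differences are normally distributed". The second is: "or non-parametrically using the Sign-Rank Test if the differences are not normally distributed". The interval is the same in both branches: "Asymptotic confidence intervals will be generated for estimates of means". The planned summaries are broader than the mean ("Continuous variables will be summarized by the mean, standard deviation, median, minimum, and maximum"), but no interval is planned for a median or pseudomedian. No normality test or threshold is named, and no significance level is set for these tests.

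The endpoints that plainly fall under the rule are the secondary change-from-baseline measures in section 5.2 at 30 days and 6, 12 and 24 months: ABI or TBI, and "Quality of Life (QoL) assessed by VascuQoL questionnaire".

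The setting is descriptive. Section 9.1 opens with "Descriptive statistics will be provided in this clinical study", and the study summary (section 2.0) says: "Designed to assess exact 95% confidence interval (CI) for primary endpoints; no formal hypothesis testing".

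**The concern.** The paired t-test and the planned interval both address the mean change, so in the first branch they agree apart from the small difference between t and normal critical values. The signed-rank test addresses symmetry about zero, in effect whether the pseudomedian is zero. When changes are skewed, the mean and the pseudomedian differ. Skewness is also what makes a normality check fail, so the plan moves to the signed-rank test in the cases where it and the mean interval part company.

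A small mean change at a late visit could then be reported with p<0.05 beside an interval that includes zero, or with p>0.05 beside an interval that excludes it. In a descriptive study the estimate and its interval are the result, and section 12.9 says the data will be used for publications, regulatory submissions and marketing. A p-value that contradicts its own interval would be hard to defend there.

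**Working it through.** **Inputs from the documents.** The test rule and the interval are from section 9.1. Section 9.3 gives 225 evaluable subjects, inflated for 10% loss: 225 / 0.90 = 250 enrolled. The plan states no error rate or power for the within-subject tests, so there is no figure of its own to reproduce.

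**Assumptions.** Shapiro-Wilk at 0.05 as the normality check; two-sided 0.05 for the tests; 95% intervals; 100 to 225 pairs per visit; skewness of the changes from 0 to 2, using centred gamma distributions (exponential at skewness 2).

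**Step 1: how far apart the two targets are.** Write δ for the distance between mean and pseudomedian in SD units. For these distributions δ = 0.042 at skewness 0.5, 0.083 at 1 and 0.161 at 2.

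**Step 2: approximate rejection rate when the mean change is zero.** If the signed-rank branch is taken and the test has about the same standard error as the mean,

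Pr(p<0.05) ≈ Φ(δ√n − 1.96) + Φ(−δ√n − 1.96).

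| Skewness | n | δ√n | Formula | Simulated, planned rule |
|---|---|---|---|---|
| 0.5 | 225 | 0.042 × 15 = 0.63 | 0.092 + 0.005 = 9.7% | 9–10% |
| 1 | 225 | 0.083 × 15 = 1.25 | 0.237 + 0.001 = 23.8% | 23–24% |
| 2 | 225 | 0.161 × 15 = 2.42 | 0.675 + 0.000 = 67.5% | 67–69% |
| 1 | 100 | 0.083 × 10 = 0.83 | 0.129 + 0.003 = 13.2% | 13–14% |
| 1 | 200 | 0.083 × 14.14 = 1.17 | 0.216 + 0.001 = 21.7% | about 21% |

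The formula matches simulation of the full two-stage rule (3,000 to 5,000 samples per setting). Because δ is multiplied by √n, the conflict grows with the sample size.

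**Step 3: simulated range for 100 to 200 pairs, true mean change zero.**

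| Skewness | Rule gives p<0.05 | p-value and mean interval disagree |
|---|---|---|
| 0.5 | about 7–9% | about 3–8% |
| 1 | 13–21% | 11–20% |
| 1.5 | 24–43% | 21–41% |

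The paired t-test rejects in about 5% of samples throughout (4–6% across runs). For the mean, the switch therefore buys no error control at these sizes.

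**Step 4: the conflict in the other direction.** Take a true mean change of +0.2 SD, right skewness 1 and n = 150, so √n = 12.25. The t-test rejects with probability about Φ(0.2 × 12.25 − 1.96) = Φ(0.49) = 69%. The pseudomedian is only 0.2 − 0.083 = 0.117 SD, so the signed-rank test rejects with probability about Φ(0.117 × 12.25 − 1.96) = Φ(−0.53) = 30%. Simulation gave 70% and 29%, with p-value and interval disagreeing in 42% of samples.

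**Step 5: where nothing goes wrong.** At n = 225:
- Pseudomedian exactly zero (the signed-rank test's own null): the rule rejects in 5.4–5.7% of samples.
- Symmetric but non-normal changes (t with 4 degrees of freedom, Laplace): 4.5–5.7%.
- Baseline and follow-up skewed but exchangeable: 4.8%, although normality was rejected in essentially every sample.

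With a true change of 0.5 SD, n = 150 and skewness of ±1, disagreement is about 0%.

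**The case against.** Four points on the other side have force.

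- **The skewness is assumed.** Nothing in the documents describes the distribution of ABI, TBI or VascuQoL change, or names Shapiro-Wilk. At skewness 0.5 the normality check fails in only some 40–70% of samples of 100 to 200, and the excess is small. This stands: the figures show what could happen over a range and do not predict this trial.
- **A reader might infer a general failure of type I error.** The documents do not support that. The signed-rank test makes no claim that the mean is zero, and against its own null it holds about 5%. The excess appears only when the mean change is zero and the changes are asymmetric, in which case something other than the mean has shifted.
- **A reader might blame the preliminary normality check.** In the skewed zero-mean cases at n = 225 the two-stage rate is within 0.3 percentage points of always using the signed-rank test. A signed-rank test fixed in advance but reported with a mean interval would give the same conflict. The pairing of test and interval is at fault.
- **A reader might infer that Rutherford Category is sent through the switch.** Section 5.2 says only "Rutherford Category at 30 days, 6, 12, & 24 months, reported as change from baseline". The switch sits in section 9.1's paragraph on continuous variables, and categorical variables have their own paragraph. The text leaves the handling of Rutherford change open; it does not impose this rule on it.

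It can also be said that mean and median will both be shown, so a divergence would be visible, and that section 9.1 leaves clarifications to the SAP. Both are true. But showing a median without an interval does not reconcile a p-value with an interval for something else, and a stated rule that can contradict itself is a proper subject for such a clarification.

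**Conclusion.** The point holds as a minor one. In the signed-rank branch, section 9.1 pairs a p-value for the pseudomedian with an interval for the mean. If changes are clearly skewed (skewness of about 1 or more) and the mean change is zero, the two would disagree in roughly 11–41% of analyses with 100 to 200 pairs; at skewness 0.5 the figure is about 3–8%. These sizes rest on the assumed gamma shapes, Shapiro-Wilk at 0.05 and two-sided 0.05 tests.

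The reach is limited. The first branch is internally consistent, and symmetric changes and large changes are not affected. The primary endpoints are binary with exact intervals (section 9.2), and no success criterion uses these tests. What is at risk is the coherence of secondary results where the mean change is small.

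**What to change.** In section 9.1, and in the SAP, replace the two-branch sentence and the interval sentence with wording to this effect: mean change from baseline in ABI, TBI and VascuQoL will be estimated at each visit with a t-based 95% confidence interval and tested with the paired t-test; the signed-rank test, with a Hodges-Lehmann estimate and its confidence interval, will be reported as a sensitivity analysis and labelled as such.

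If the sponsor prefers the pseudomedian as the target, the signed-rank test with the Hodges-Lehmann estimate and interval would cure the mismatch equally well, provided the choice is fixed in advance for each endpoint.

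An optional clarification is to state how Rutherford Category change will be shown, for example by a shift table and the proportion improved by at least one category with an exact interval.

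The cost is two sentences. No extra data, visits or subjects are needed.

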### 9.2 Primary Endpoints

Exact 95% confidence intervals will be generated for primary endpoints and estimates of proportions.

#### 9.2.1 Primary Safety Endpoint

The primary safety endpoint is Major Adverse Limb Events (MALE) or Post-Operative Death (POD) at 30 days defined as a composite of:

- all-cause death
- above-ankle amputation of the index limb
- major reintervention (new bypass graft, jump/interposition graft revision, or thrombectomy/thrombolysis) of the index limb involving a BTK artery

#### 9.2.2 Primary Effectiveness Endpoint

The primary effectiveness endpoint is Procedure Success defined as ≤50% residual stenosis for all treated target lesions without serious angiographic complications (flow-limiting dissection, perforation, distal embolization, or acute vessel closure) as assessed by the angiographic core lab at the final timepoint.

	No.: CP 65007	REV. C
	TITLE: Disrupt PAD BTK II Study	
	CLASS: CLINICAL PROTOCOL	PAGE 41 OF 71

### 9.3 Sample Size Determination

The sample size was calculated based on the precision of the exact 2-sided 95% confidence interval (CI) of the primary effectiveness endpoint, using the LIBERTY 360 study results as a reference. The LIBERTY 360 study of endovascular interventions for PAD is one of the largest, real-world, core laboratory–adjudicated studies to include patients with varying degrees of PAD severity. Procedural Success for the RC 4-5 cohort of this large contemporary data set was 75.8% [71.9, 79.3] [20].

The calculation of the Disrupt PAD BTK II sample size was based on a procedural success estimate of 75.8%. Combined with a desired precision of +/- 5.8% and an alpha of 0.05 (95% CI), a sample size of 225 was selected to provide a probability width (“power”) of 0.827. Assuming a lost-to-follow-up rate of 10%, up to 250 subjects will be enrolled.

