### 9.4 Populations for Analysis

The primary analysis population will be the Intent-to-Treat (ITT) cohort which includes all enrolled subjects.

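### Section 9.3 claims probability 0.827 of reaching ±5.8 points with 225 subjects, but the exact interval it names gives 0.51

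*Combined protocol and SAP*

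**What the plan says.** Section 9.3 names the method: "The sample size was calculated based on the precision of the exact 2-sided 95% confidence interval (CI) of the primary effectiveness endpoint". It assumes a Procedure Success rate of 75.8%, taken from a reference study of endovascular interventions. It then sets the precision and alpha: "Combined with a desired precision of +/- 5.8% and an alpha of 0.05 (95% CI), a sample size of 225 was selected". The same sentence attaches the probability: "a sample size of 225 was selected to provide a probability width (“power”) of 0.827". A 10% allowance for loss to follow-up raises 225 to at most 250 enrolled.

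The analysis sections name the same interval. Section 9.2: "Exact 95% confidence intervals will be generated for primary endpoints and estimates of proportions". The Study Summary (section 2.0): "Designed to assess exact 95% confidence interval (CI) for primary endpoints; no formal hypothesis testing". Section 9.1 also plans exact intervals for proportions and keeps asymptotic intervals for means. No normal-approximation interval for a proportion appears anywhere.

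**The concern.** With no hypothesis test, the expected width of the interval is the whole case for the sample size, and 0.827 is the only probability given in support of it. A reader takes it as roughly a five-in-six chance that the reported exact interval will be no wider than ±5.8 points.

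The exact interval is wider than the Wald interval at the same count. A probability worked out for one does not carry over to the other, and near the planning rate a small difference in width moves the probability a long way. If 0.827 does not belong to the exact interval, section 9.3 overstates the assurance for the interval that will be reported.

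**Working it through.** **Inputs (all from section 9.3).** n = 225 evaluable; true rate p = 0.758; half-width limit h = 0.058; two-sided 95% interval; stated probability 0.827; 10% loss.

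**Quantity.** Let X ~ Binomial(225, 0.758). For each count x, compute the 95% limits L(x) and U(x) and the half-width (U − L)/2. The probability sought is the sum of P(X = x) over all x with half-width ≤ h. Near p = 0.758 the half-width shrinks as x rises, so the sum reduces to P(X ≥ x₀), where x₀ is the first count that meets the limit. Very low counts also qualify, but their probability is negligible.

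**Step 1: reproduce 0.827.** Wald half-width = 1.96 × √[(x/225)(1 − x/225)/225].
- x = 164: 0.05808, above the limit.
- x = 165: 1.96 × √(0.7333 × 0.2667/225) = 0.05778, within it.
- So x₀ = 165 and P(X ≥ 165) = 0.8273, which matches the stated figure.

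**Step 2: the exact interval.** The Clopper-Pearson limits are L = the 2.5% quantile of Beta(x, 226 − x) and U = the 97.5% quantile of Beta(x + 1, 225 − x).
- x = 170: 0.6940 to 0.8102, half-width 0.05810, above the limit.
- x = 171: 0.6987 to 0.8143, half-width 0.05776, within it.
- So x₀ = 171 and P(X ≥ 171) = **0.5085**.

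The expected count is 225 × 0.758 = 170.55, right at this threshold, and the mean exact half-width is 0.0577. So ±5.8 points is about the average exact width, which is why the chance of meeting it is near one half.

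**Step 3: where the exact interval does give 0.827.** At x = 165 the exact half-width is 0.05971; at x = 164 it is 0.06001. A limit of 0.060 therefore also has x₀ = 165 and gives 0.8273. Exact probabilities for other limits:

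| Half-width limit | Exact probability, n = 225 |
|---|---|
| 0.058 | 0.5085 |
| 0.059 | 0.6862 |
| 0.0595 | 0.7856 |
| 0.060 | 0.8273 |

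**Step 4: other explanations.**
- Rounding: with p from 75.75% to 75.85% and h from 5.75 to 5.85 points, the exact probability runs from 0.44 to 0.64.
- Conditioning on the exact interval covering p: 0.511.
- Asymmetry of the exact interval: limiting only the lower arm to 5.8 points gives 0.058; limiting only the upper arm gives 0.939.
- Wilson, Agresti-Coull, Jeffreys or mid-P interval at 5.8 points: 0.863 each. Wilson returns 0.8273 at a limit of 5.75 points, but it is not the interval named either.

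Any pairing of method and limit with x₀ = 165 yields the same number, so the match alone cannot identify the origin.

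**Step 5: sensitivity of the exact probability at ±5.8 points.**

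| Evaluable n (p = 0.758) | 225 | 230 | 239 | 245 | 250 |
|---|---|---|---|---|---|
| Probability | 0.51 | 0.62 | 0.84 | 0.91 | 0.96 |

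| True rate (n = 225) | 0.74 | 0.758 | 0.78 | 0.80 |
|---|---|---|---|---|
| Probability | 0.27 | 0.51 | 0.79 | 0.94 |

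**Step 6: enrolment.** 225/(1 − 0.10) = 250, as stated.

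**The case against.** The strongest reply is that the figures are consistent with one another under a Wald interval, to three decimals, so the conflict is between one label and one number. The ±5.8 points is also close to the average exact half-width at 225; only the probability attached to it fails. Both points are fair. They describe how the error may have arisen, but they do not make 0.827 correct for the interval that sections 9.1, 9.2 and 9.3 and the Study Summary all name.

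The second reply is that little depends on it. There is no hypothesis test, and an exact interval will be reported whatever its width. Procedure Success is read at the end of the procedure, and section 9.4 says that "The primary analysis population will be the Intent-to-Treat (ITT) cohort which includes all enrolled subjects", so loss to follow-up should remove few subjects from this endpoint. With all 250 evaluable the exact probability is 0.96, above the stated figure, although 250 is a ceiling rather than a commitment. The true rate may also exceed 75.8%. Section 3.1.2 reports 99% of lesions below 50% residual stenosis in an earlier cohort, which is a per-lesion result and not the same endpoint. At a true rate of 0.90 the exact probability with 225 subjects is above 0.999. All of this stands and limits the consequence. It does not repair the statement, which is tied to 225 subjects and a rate of 75.8%.

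**Conclusion.** The concern holds. At 225 evaluable subjects and a true rate of 75.8%, the exact 95% interval has half-width at most 5.8 points with probability 0.51, which is 0.32 below the stated 0.827. This takes precision to mean half the total width of a Clopper-Pearson interval; the alternative readings tried for that interval do not recover 0.827 either. The origin is either a different interval method or a misstated half-width, and the protocol does not settle which.

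Measured in width the error is small: the exact interval needs a limit just above 5.97 points, about 0.17 more than stated, to reach 0.827. It is a reporting error that should be corrected. It does not threaten the study's conclusions.

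**What to change.** State in section 9.3 which interval and half-width produced 0.827, then give the figures for the exact interval that will be reported. Suggested wording: *With 225 evaluable subjects and a true rate of 75.8%, the exact two-sided 95% CI has half-width ≤6.0 points with probability 0.83 (≤5.8 points with probability 0.51; 0.96 if all 250 are evaluable).*

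Keep 225 evaluable and 250 enrolled. Holding both ±5.8 points and 0.827 for the exact interval would take about 239 evaluable subjects (0.84), or 239/0.90 = 265.6, so 266 enrolled; a descriptive study does not need that.

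The cost is one sentence. Enrolment, endpoint, analysis and reported interval do not change. The only visible effect is that the half-width quoted alongside 0.83 becomes 6.0 points instead of 5.8.
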